3 SUMMARY TABLES, LISTINGS, AND FIGURES

3.1 General Conventions

Unless otherwise stated, summary statistics including the number of subjects (n), mean, standard deviation, median, minimum, and maximum will be presented for continuous variables. Generally, the minimum and maximum values will be presented to the same decimal precision as the raw values, the mean and median values to one more, and the standard deviation, to two more decimal places than the raw values. For categorical variables, per category, the absolute counts (n) and percentages (%) of subjects with data will be presented. Percentages will be presented to one decimal place.

For AEs, medical history and concomitant medications will be reported on a per-subject basis. The denominator for the percentage calculation will be the number of subjects at risk in each treatment group. A subject will be considered at risk if the subject is in the analysis set and in the subgroup of interest.

All p-values will be rounded to 4 decimal places. If a p-value is less than 0.0001 it will be displayed as “< 0.0001”, a p-value rounding to 1 will be displayed as “> 0.9999”.

3.2 Clinical Study Subjects

3.2.1 Subject Disposition and Analysis Populations.

The number of subjects treated and discontinued early (i.e., follow-up visit was not completed), will be summarized. The reason for early termination will be summarized. Additionally, a summary of subjects who attended each visit result will be produced.

A listing of entry criteria that were not met will be produced. The listed criteria will include the criteria language. A table of the violated entry criteria for subjects will be produced, as well as a table that summarizes the screen failure reasons for screen failure subjects.

The number of subjects in each analysis population will be summarized.

3.2.2 Demographics and Baseline Characteristics

Demographic and baseline characteristics will be summarized descriptively. This will include the following items:

- Age at informed consent
- Race
- Ethnicity
- Sex
- Height
- Weight

HighTide Biopharma Pty. Ltd.
Protocol HTD1801.PCT013

- BMI
- Duration of Primary Biliary Cholangitis
- Biochemical evidence of Cholestasis (Yes or No)
- Age of initiation of UDCA
- Age at diagnosis of PBC
- Most recent UDCA dose (mg/kg/day)
- Presence of antimitochondrial antibody
- Historical ALP
- Pruritus VAS

3.2.2.1 Baseline Laboratory Assessments

Baseline laboratory assessments will be summarized descriptively. This will include:

- ALP
- GGT
- Total Bilirubin
- AST
- ALT
- Albumin
- Platelets
- AMA (Positive, Equivocal, or Negative)
 - For positive values, AMA will also be summarized as a continuous measure
- ANA (Positive, Equivocal, or Negative)
 - For positive values, ANA will also be summarized as a continuous measure

3.2.3 *Concomitant Medications*

Medications with a stop date before the treatment dosing date will be considered prior medications/procedures. Medications with a start or stop date on or after the treatment dosing date will be considered concomitant. All medications marked as ongoing are concomitant.

A medication with an incomplete stop date will be considered concomitant if:

- Month is missing and year is equal to or after the year of treatment dosing date
- Day is missing and year is equal to the year of the treatment dosing date and month is equal to or after the month of the treatment dosing date.

HighTide Biopharma Pty. Ltd.
Protocol HTD1801.PCT013

All concomitant medications will be summarized by preferred terms in descending order of frequency. All medications, including prior and prohibited medications, will be provided in a listing.

3.2.4 *Medical History*

Medical history will be tabulated by system organ class and preferred terms and provided in a listing.

3.2.5 *Clinical Study Treatment and Extent of Exposure*

The total tablets used, duration of treatment, and compliance (see Section 2.2) will be summarized. Average dose received per day, along with the number of subjects with dose interruption or modification will also be summarized.

3.3 *Analysis of Efficacy Endpoints*

3.3.1 *Serum Alkaline Phosphatase*

The serum ALP levels, change from baseline, and percent change from baseline will be summarized with descriptive statistics by timepoint for the ITT and PP populations. The summary measures will include 95% normal distribution confidence intervals of the treatment difference. In addition, a t-test will be performed for the percent change from baseline to Week 12. Subgroup analyses (see Section 2.5.1.2) will be performed for the change from baseline and percent change at Week 12 data.

The proportion of subjects who have $\geq 20\%$ and the proportion with a $\geq 40\%$ decrease in ALP from Baseline will be summarized at each timepoint with Week 12 being the study specified timepoint. Additionally, the proportion of subjects who normalize ALP will be summarized by timepoint.

3.3.2 *Secondary Endpoints*

Tables for the secondary endpoints, see below, will be summarized for the respective laboratory values and the change from baseline results at each timepoint. Total bilirubin and GGT will be summarized within the ITT and PP populations. Subgroup analyses for specified laboratory parameters (see section 2.5.2) will be performed for the change from baseline and percent change at Week 12. Central and local lab data will be used for the efficacy analyses.

- Total bilirubin
- GGT
- ALT
- AST
- Total cholesterol

- LDL
- Triglyceride
- Fibrinogen
- CRP
- Haptoglobin
- ELF
- Immunoglobulins (IgM and IgG)

3.3.3 *UDCA Use*

A plot of average percent change in ALP at each timepoint through Week 12 for groups defined by the ratio of current to prior dose of UDCA. The ratio groups displayed in the plot will be <90%, 90% to 110%, and >110%. Separate subject level plots will also be presented for each ratio group through Week 12.

3.3.4 *ELF Score*

The number of subjects within ELF score interpretations will be presented at Week 12 as well as the shift within categories for change from baseline to week 12. Summary statistics at Week 12 will also be presented.

3.3.5 *GLOBE Score*

The number of subjects within GLOBE score interpretations will be presented along with the Fibrosis Score interpretations. Change in GLOBE score from baseline will be summarized using descriptive statistics at Week 6 and Week 12. A listing of the GLOBE score will also be produced and summarized by duration of UDCA exposure.

Survival risk (%) for 5, 10, and 15 years will be summarized using descriptive statistics at Week 12 for the GLOBE Scores.

3.4 *Analysis of Safety Endpoints*

Safety Endpoints (Adverse Events, Clinical Laboratory Results, Vital Signs) will be presented at the scheduled timepoints as outlined in Table 1, with further detail in the protocol.

3.4.1 *Adverse Events*

An overview of AEs, which includes subject incidence of TEAEs, treatment-related TEAEs, serious TEAEs, AESIs, TEAEs by CTCAE grade and TEAEs leading to permanent discontinuation of treatment. For TEAEs presented by CTCAE grade, the worst grade during the clinical study will be presented for each subject.

The subject incidence of TEAEs, treatment-related TEAEs and TEAEs leading to permanent discontinuation of treatment will be summarized by system organ class and preferred term.

HighTide Biopharma Pty. Ltd.
Protocol HTD1801.PCT013

TEAEs will also be summarized in a table by CTCAE grade. For TEAEs presented by CTCAE grade, the worst grade for each event during the clinical study will be presented for each subject. A listing for all off-treatment AEs will be presented similarly.

All AEs will be presented as a listing by subject. TEAEs leading to treatment discontinuation will be provided in a separate listing.

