### 7.3. Participant Discontinuation/Withdrawal from the Study

Subjects may be discontinued from the study for any of the following reasons:

- Noncompliance
  - Failure to receive study medication or treatment
  - Failure to comply with protocol requirements
  - Unauthorized, subject-initiated changes in dosing regimen
- Withdrawal of consent
  - Any subject who withdraws consent for any reason at any time during the study will be discontinued from the study, and the reason(s) will be documented on the appropriate eCRF page.
- Lost to Follow-Up

- For subjects who cannot be contacted for either a return for a scheduled clinic visit or for follow-up assessments as described, and who may be considered “lost to follow-up,” at least 3 documented attempts should be made to establish contact with and to instruct the subject on how to complete study procedures. In the final attempt to contact the subject, a letter should be sent by certified mail to the subject’s last known address
- Adverse Events
  - Study drug will be discontinued in an individual subject if the subject experiences a grade 3 and above adverse event (AE) for which the causality is considered as related to investigational study drug
- Treatment Failure
  - If any subject fails treatment after having their dose of HTD1801 reduced, their participation in the study will be ended and they will be allowed to resume their pre-study treatment for PBC. A subject will be deemed to have failed treatment if serum ALP, after having been lowered on initial treatment, returns to baseline or higher on two subsequent occasions (baseline being the average of the historical value and the value at screening).

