### 12.4. Statistical Analyses

#### 12.4.1. General Approach

Endpoints will be summarized using descriptive statistics. For continuous variables n (number of subjects with data), mean, standard deviation, median, minimum, and maximum will be used. For categorical results the number of subjects and the percent of subjects per category will be summarized. Confidence intervals will be generally reported using 95% two-sided confidence intervals. When testing is used p-values with four decimal places will be reported; no adjustment for multiplicity will be conducted.

Missing data will not be imputed for the efficacy analyses. Missing dates for adverse events and concomitant medication will be imputed to allow these items to be summarized as on or off treatment.

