2.6 Handling of Missing Data

Summary statistics will generally be reported based upon observed data. Missing data will not be imputed for the efficacy analyses. Percentages will be reported for subjects with data. Missing dates for AEs and concomitant medications will be imputed to allow these items to be summarized as pre-treatment or not. Should a determination of treatment period (on treatment or pre-treatment) be required for AEs or concomitant medication, but the corresponding date is missing or partial, the event/medication will be considered on treatment unless the portions of the date that are available indicate this is not possible.

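### SAP 3.2.3: the missing-day stop-date rule fails across a year end, in conflict with SAP 2.6 and 2.7, and the medication table does not separate use begun after the last dose

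*SAP*

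**What the plan says.** SAP 3.2.3 sorts medications by their dates relative to first dosing.

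- Prior: "Medications with a stop date before the treatment dosing date will be considered prior medications/procedures".
- Concomitant: "Medications with a start or stop date on or after the treatment dosing date will be considered concomitant".
- Ongoing: "All medications marked as ongoing are concomitant".
- Incomplete stop date, first bullet: concomitant if "Month is missing and year is equal to or after the year of treatment dosing date".
- Incomplete stop date, second bullet: concomitant if "Day is missing and year is equal to the year of the treatment dosing date" and the stop month is the dosing month or later.

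Three other places bear on the same classification.

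- SAP 2.6, for a missing or partial date: "the event/medication will be considered on treatment unless the portions of the date that are available indicate this is not possible". It distinguishes pre-treatment from everything else and has no post-treatment class.
- SAP 2.7 gives a general rule: a medication is concomitant if it had not ended before treatment began.
- Protocol 12.4.1: "Missing dates for adverse events and concomitant medication will be imputed to allow these items to be summarized as on or off treatment".

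SAP 3.2.3 also promises a listing of every medication, including prior and prohibited ones. The SAP does not say which of sections 2.6, 2.7 and 3.2.3 governs when they differ.

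**The concern.** The two incomplete-date bullets stand next to each other and differ in one respect. The month-missing bullet accepts the dosing year or any later year; the day-missing bullet accepts the dosing year only. A 12-week course begun late in the year runs into the next one, so the day-missing bullet can leave out a drug that was being taken together with HTD1801.

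The secondary point is that the rule is bounded only at first dose. Medications are collected through the Week 16 visit, 28 days after the last dose, so a drug started in that period goes into the same table as one taken on treatment. Resumed UDCA is the natural example. For treatment failure after a dose reduction, Protocol 7.3 says of subjects that "their participation in the study will be ended and they will be allowed to resume their pre-study treatment for PBC".

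In a single-arm trial with an ALP endpoint, the concomitant-medication table is where a reader looks to see whether other drugs active against PBC were taken alongside HTD1801. What is at stake is the accuracy of that table.

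**Working it through.** The plan gives no figure on this point to reproduce, so the check applies the written rules to example records and then counts how many date combinations are exposed.

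**Year-end case.** Take an illustrative first dose on 15 November 2021 and a drug begun earlier, not marked ongoing, and stopped in January 2022. With SAP study day equal to date minus first-dose date, 1 January is Day 47 (16 + 31) and 31 January is Day 77. Every possible January stop day therefore falls within the 84-day treatment period.

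| Stop date as recorded | SAP 3.2.3, literal | SAP 2.6 | SAP 2.7 |
|---|---|---|---|
| 10 January 2022 | concomitant | not needed, date complete | concomitant |
| January 2022, day missing | **not concomitant** (2022 is not 2021) | on treatment | concomitant |
| 2022, day and month missing | concomitant | on treatment | concomitant |

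The middle row is the anomaly: a more complete date is left out while a less complete one is counted.

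**Conditions needed.** All of the following must hold:

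1. the drug began before first dose, or its start is unknown (a later start makes it concomitant by start date);
2. it is not marked ongoing;
3. the stop month is known and the stop day is missing;
4. the stop falls in a calendar year after the dosing year.

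**Exposure.** Assume first-dose dates spread evenly over a 365-day year. Day 84 falls in the next year for first doses from 9 October (23 + 30 + 31 = 84 days to 31 December) through 31 December. That is 84 of 365 = 23.0%.

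Assume also that stop days are spread evenly over Days 0 to 84. There are 365 × 85 = 31,025 combinations of first-dose date and stop day. A first dose on 9 October has 1 stop day in the next year, and one on 31 December has 84. The literal day-missing bullet therefore misses 1 + 2 + … + 84 = 84 × 85 / 2 = 3,570 combinations, or 3,570/31,025 = 11.5%. This is a share of records that already meet conditions 1 to 3. With complete dates, with the month missing too, or under SAP 2.6, the number missed is 0. It is also 0 if the bullet accepts a later year.

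**Upper-limit case.** Suppose the last dose is on Day 40 and UDCA is restarted on Day 42. The start date is after first dose, so SAP 3.2.3 gives concomitant. The restart is 42 − 40 = 2 days after the last dose, and SAP Table 2 treats anything more than 1 day after the last dose as off treatment. SAP 3.4.1 provides a listing of off-treatment adverse events; medications have no matching separation.

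**The case against.** **The year-end wording.** The bullets say when a medication is concomitant; they do not say it is concomitant only then. A stop in January 2022 with the day unknown cannot precede a November 2021 first dose, so it is not prior. It also arguably satisfies the general on-or-after rule whatever the day was, and SAP 2.6 and 2.7 both include it. This stands in part: a reader might infer that overlapping drugs will certainly be lost, and the documents do not support that. It does not remove the conflict. SAP 3.2.3 is the section that specifies the table, its bullets are written as the test for incomplete dates, and a programmer who codes them literally will exclude the record. No order of precedence is stated.

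**The missing upper limit.** The protocol itself records concomitant medications at Week 16, and Protocol 6.4.2.1 prohibits UDCA, obeticholic acid and the fibrates until 28 days after completion. Showing follow-up use in the table fits that window. The sentence in Protocol 12.4.1 explains why dates are imputed and does not promise a post-treatment table. This stands to the extent that pooling is not plainly an error; what remains is a difference in wording and a table that cannot show the distinction.

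**The consequence.** A reader might also infer that resumed UDCA distorts the efficacy result. It does not follow. SAP 2.5.1.1 limits the primary analysis to on-treatment Week 12 results, and no efficacy analysis uses the concomitant classification. Every medication is listed in any case.

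**Conclusion.** The concern holds in a limited form. Read literally, the day-missing bullet in SAP 3.2.3 gives a wrong answer for one narrow kind of record and conflicts with SAP 2.6, SAP 2.7 and its own neighbouring bullet. Secondarily, the absence of a limit at the last dose means that the table cannot separate on-treatment from post-treatment use.

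The effect is confined to a descriptive table; the primary ALP analysis, its significance level and its power are untouched. How many records will be affected is unknown, because the documents do not say how often stop days will be missing. The 23% is the share of 84-day treatment periods that cross a year end under uniform first-dose dates, and the 11.5% additionally assumes evenly spread stop days. Neither is a misclassification rate for the trial. Nor is the share of a completer's time spent off drug (28 of 112 days, 25%), which counts days and not medications or subjects. This is a minor correction, worth making because it is nearly free.

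**What to change.** 1. Reword the day-missing bullet in SAP 3.2.3 so that the medication is concomitant when the stop year is later than the first-dose year, or when the years match and the stop month is not earlier than the first-dose month.
2. State that SAP 2.6 governs any other partial date, so that sections 2.6, 2.7 and 3.2.3 give one answer.
3. Add a flag for medications whose start date is more than 1 day after the last dose, the limit already used in SAP Table 2, and show them separately as post-treatment. Base the flag on the start date: a test on the stop date alone would put a drug begun after the last dose back among the on-treatment ones.

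The cost is a few sentences of SAP text, a small programming change and one derived flag or extra table section. No new data are needed: medication dates and the treatment end date are already used in the SAP.

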#### **10.1.3. Process for DILI Monitoring**

Serum ALT will be measured as part of a serum chemistry panel at screening, baseline and at weeks 2, 4, 6, 8 and 12. Serum samples will be shipped to a central or local laboratory for testing. Central lab reports will be faxed or emailed to the clinical site within 24 hours of receipt of the sample to be reviewed by the site PI. Local lab results will need to be entered into eDC. Values meeting or exceeding the DILI threshold described in Tables 7 and 8 will be flagged for the attention of the medical monitor. The medical monitor will contact the clinical site to initiate the DILI monitoring protocol.

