1.5 Decision Rule and Sample Size

The significance level for this study is 5% (one-sided). If the one-sided p-value is less than 5% then the null hypothesis of no treatment effect is rejected.

A sample size of 30 subjects provides $\geq 90\%$ power for the primary endpoint assuming a mean percent reduction in ALP of 15% and a standard deviation of 25%. Power calculations use a 5% one sided alpha and a t-test. Sample size calculation were performed in PASS.

At least 6 subjects will participate in a PK sub study.

2 STATISTICAL METHODS**2.1 Analysis Populations**

The following analysis populations will be defined for statistical analysis:

- Screened population - All subjects who sign the study informed consent.
- Intention-to-treat (ITT) population - All subjects that receive at least one dose of HTD1801. This population will be used for the primary endpoint, as well as all efficacy, safety, and baseline/demographic analyses and summaries.
- Per Protocol (PP) Population – All subjects in the ITT population who provide a Week 12 assessment and 80% study drug compliance. This population will be used for selected efficacy analyses and summaries.

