2.3.1 Alkaline Phosphatase

ALP results are provided by the central and local laboratory with units of Units per Liter (U/L). Baseline is defined as the last available ALP result prior to treatment with change from baseline and percent change from baseline based upon this baseline value as the respective timepoint. Normalized ALP is defined as having ALP within the normal range (37 U/L to 116 U/L). Historical ALP will be summarized in the baseline characteristics table but not used otherwise.

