2.4 Study Day and Visit Windows

Summary tables will report data based upon the protocol scheduled time points (Baseline, Weeks 2, 4, 6, 8, 12, 16). Assessment will be assigned to these time points based upon the study day they are performed on. Study day is defined as

$$\text{Study Day} = \text{date of assessment} - \text{date of first treatment}.$$

The analysis windows used to report endpoints are outlined in Table 2. Assessments are assigned to an analysis window based upon the study day it occurred on as well as the treatment status at the time the assessment was performed. If more than one assessment is available within the range, the assessment closest to the target day is reported for the analysis window. If two observations exist with the same distance to the target day, the first observation is used.

Table 2 Analysis Windows

Visit	Study Day Range	Target Day	Treatment Status
Screening	< Day -1	First	Off Treatment ^a
Baseline Visit	Day 1	Day 1	Off Treatment ^a
Week 2	Day 2 to Day 21	Day 14	On Treatment ^b
Week 4	Day 22 to Day 35	Day 28	On Treatment ^b
Week 6	Day 36 to Day 49	Day 42	On Treatment ^b
Week 8	Day 50 to Day 70	Day 56	On Treatment ^b
Week 12	Day 71 to Day 90	Day 84	On Treatment ^b
Week 16	> Day 90	Day 112	Off Treatment ^c

^a Prior to first treatment.

^b After the start of treatment to 1 day after the last dose.

^c More than 1 day after the last dose.

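### SAP 2.3.1 and 2.4 rank neither central over local ALP results nor scheduled over unscheduled ones, so a local value can displace the central Week 12 value or be paired with a central baseline

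*SAP*

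**What the plan says.** **Source of ALP.** SAP 2.3.1 is the direct anchor for the primary endpoint: "ALP results are provided by the central and local laboratory with units of Units per Liter (U/L"). Percent change is taken from the last result before treatment. SAP 3.3.2 states more generally that "Central and local lab data will be used for the efficacy analyses"; that sentence stands under the secondary endpoints, whose analyte list omits ALP.

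**Choice among several results.** Under SAP 2.4, "the assessment closest to the target day is reported for the analysis window", and the earlier result wins a tie. Table 2 sets Week 12 as Day 71 to 90, target Day 84, on treatment up to 1 day after the last dose. Neither laboratory nor scheduled status enters the rule.

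**Where local results come from.** Protocol 10.1.3 lists chemistry at screening, baseline and Weeks 2, 4, 6, 8 and 12, and continues: "Serum samples will be shipped to a central or local laboratory for testing". Protocol Tables 7 and 8 allow local repeat panels, which include ALP, for subjects living far from the site; these are entered as unscheduled visits. Protocol 11.2 allows a local draw at Early Termination.

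**What is absent.** Neither document gives central results priority, requires one laboratory for both time points, or plans a central-only sensitivity analysis.

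**The concern.** Percent change from baseline is meant to compare a subject with himself or herself. If the two values come from laboratories that read differently, the difference between them enters the primary endpoint as if it were a drug effect, or a loss of one. The nearest-day rule makes this possible even when a scheduled central Week 12 result is in hand, because a local result a day or two nearer Day 84 takes its place. The same mixing can move a subject across the 20% or 40% responder cut-offs. The study is open-label, so the order of preference between two known results should be fixed in advance.

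**Working it through.** **1. The plan's own figure.** Inputs from SAP 1.5: 30 subjects, mean change -15%, SD 25%, one-sided 5% t-test. The noncentrality is (15/25) × √30 = 3.29 with 29 degrees of freedom. The exact power is 94.1%, consistent with the stated 90% or more. The standard error of the mean is 25/√30 = 4.56 points.

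**2. Routes into the Week 12 window.**
- Chemistry sent to a local laboratory under protocol 10.1.3. This can create a mixed pair.
- A local liver-monitoring repeat under protocol Tables 7 and 8 while study drug continues. This can displace a scheduled central result.
- A local Early Termination draw on Day 71 to 90, within 1 day of the last dose. SAP 2.4 assigns it to Week 12, where it can be paired with a central baseline.

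**3. When displacement occurs.** The protocol allows the Week 12 visit on Day 84 ± 3. Applying the SAP 2.4 rule, with the last dose on the visit day:

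| Central sample | Local sample that replaces it |
|---|---|
| Day 81, 82 or 83 | only one taken the next day |
| Day 84 | none |
| Day 85 | Day 83 or 84 |
| Day 86 | Day 82 to 85 |
| Day 87 | Day 81 to 86 |

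For a central sample on Day 86, a local one on Day 84 is 0 days from target against 2, so it is chosen. Day 82 also wins: both are 2 days away and the earlier is taken.

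**4. Effect on one subject.** Let r be the ratio of local to central reading and c the true change. The observed change is r(1 + c) - 1. The documents give no r; 0.80 to 1.20 is assumed.
- r = 0.90: no true change appears as -10%; a true -15% appears as 0.90 × 0.85 - 1 = -23.5%.
- r = 1.10: no true change appears as +10%; a true -15% appears as 1.10 × 0.85 - 1 = -6.5%.
- A true -15% counts as a 20% responder if 0.85r ≤ 0.80, that is r ≤ 0.941.

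**5. Effect on the trial mean.** With k mixed pairs of 30, the shift is (k/30)(r - 1)(1 + c). With no true change:
- r = 0.80: -0.7, -2.0 and -4.0 points for k = 1, 3 and 6.
- r = 0.90: -0.3, -1.0 and -2.0 points.
- Ratios of 1.20 and 1.10 give the same sizes with the opposite sign.

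One pair at the edge of the range therefore moves the mean by 20/30 = 0.67 points, or 0.67/4.56 = 0.15 standard errors.

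**6. Effect on the test.** Simulation with 200,000 trials per scenario, normally distributed percent change with SD 25, and k subjects' Week 12 values multiplied by r, all in the same direction. The counts k are assumptions too.

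| Quantity | r | k = 1 | k = 3 | k = 6 |
|---|---|---|---|---|
| Type I error (nominal 5%) | 0.90 | 5.7% | 7.5% | 11.0% |
| Type I error | 0.80 | 6.5% | 10.5% | 20.2% |
| Power at -15% (94.1% unmixed) | 1.10 | 93.2% | 90.9% | 87.0% |
| Power at -15% | 1.20 | 91.9% | 86.4% | 74.8% |

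With r = 1, the simulation returns about 5% and 94%, as it should.

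**The case against.** The strongest reply is that this will hardly ever happen at Week 12. The visit is in-clinic (protocol 8.7), its chemistry panel carries no home-draw footnote in protocol Table 1, and protocol 11.2 omits it from the contingency visits. Protocol 9.2.6 names a central laboratory for scheduled safety assessments. Local contingency results are mapped to the visit they replace, so they stand in for a central sample and do not compete with one. Local liver-monitoring repeats need an ALT event and a subject living remotely. Subjects who meet a stopping criterion leave treatment, and the on-treatment condition then excludes results more than 1 day after the last dose. Both documents also call the tests descriptive. All of this stands as an argument about frequency and size. It does not supply the missing rule: protocol 10.1.3 still allows local testing in a paragraph that lists Week 12, and SAP 2.4 still ignores the laboratory.

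A reader might infer more than the documents support:
- **That dose-reduced subjects are especially exposed.** Protocol 6.1.3 and 7.1 require ALP every 2 to 4 weeks, but do not say that these samples are local or extra. The ordinary visits already meet that interval.
- **That inclusion criterion 4c concedes the problem.** It concerns reference ranges for historical values, not measured activity on study. SAP 2.3.1 uses historical ALP only as a baseline characteristic.
- **That the error rivals the planned 15% effect.** Assumed local ULNs of 100 to 130 U/L against the central 116 give 100/116 - 1 = -13.8% to 130/116 - 1 = +12.1%, if measured activity scales with the ULN. That is one subject's error set against a group mean; at the extreme, one pair moves the mean by 13.8/30 = 0.46 points.

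**Conclusion.** The gap is real: as written, the SAP lets a local ALP result displace the scheduled central Week 12 result or be paired with a central baseline, and nothing else in the documents prevents it. It is probably infrequent. Under the assumed ratio of 0.80 to 1.20, one mixed pair of 30 shifts the mean by at most about 0.7 points. The larger distortions need 3 to 6 pairs, all biased in the same direction, and nothing in the documents shows that this is likely. The stated power is not in question. The case for change rests on a clear rule being available at almost no cost, not on an expected large bias.

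**What to change.** In SAP 2.4, with a matching sentence in 2.3.1, state for the primary and all other ALP endpoints that:

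1. the central-laboratory result in the analysis window is used whenever one exists, even if a local result is nearer the target day;
2. a local result is used only when the window holds no central one;
3. the nearest-day and tie rules apply within the preferred source.

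Add a sensitivity analysis of the primary endpoint restricted to subjects with central results at both baseline and Week 12.

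Do not rescale by ULN in the primary analysis. If two laboratories read the same U/L but quote different limits, rescaling creates the error it is meant to remove: with assumed local ULNs of 100 and 130, no change becomes 116/100 - 1 = +16.0% and 116/130 - 1 = -10.8%. It would also change the endpoint for some subjects.

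The cost is SAP wording, one selection rule in programming and one extra table. The downside is an occasional value slightly further from Day 84.
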